therapy for TS patients. This paradigm is preferable to chronic stimulation for its potential to reduce stimulation-related side effects. Outcomes will be measured by comparing the results of chronic continuous stimulation (Specific Aim 1) to an acute test of responsive stimulation (Specific Aim 3). Responsive stimulation parameters will be identical to chronic continuous stimulation parameters and will strictly be within safety ranges. If acute responsive stimulation leads to low side effects and comparable clinical outcomes for a patient, we will test chronic responsive stimulation for one week at a time, up to four weeks in total. This procedure will be performed at an appropriate time point (approved by the Principal Investigator) after the 6 month primary endpoint is reached but prior to Month 36 (study completion) (see visits 6.1-6.4 in schedule of events). The patient programmer will allow patients to turn off responsive stimulation and switch back to standard continuous therapy. A firmware update from Medtronic will allow the Summit RC+S internal signal sensing and processing units to communicate with the stimulation unit. Outcomes for chronic responsive stimulation will also be measured by comparing the results of chronic continuous stimulation.

Duration of the Investigation: We expect the duration of this investigation will be five years. In the first year we plan to implant and follow the first two subjects. In Year 2 we will plan to implant and follow the third, fourth, and fifth subjects while we continue to follow the first two subjects. In Year 3 we plan to implant and follow the sixth and seventh, and eighth subjects while we continue to follow the first five subjects. In Year 4 we plan to implant and follow the ninth and tenth subject, but also to continue to follow the other eight subjects. In Year 5 we will complete follow-up

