and data analysis and submit publications for peer review. These time estimations are plans that could be subject to change based on a number of external factors that may be out of our control. We plan to follow each subject clinically for a minimum of 24 months following implant, and to follow them for 12 more months for a minimum of 2 and a maximum of 4 research visits, and then clinically each year as long as they wish to remain implanted, and to assess needs for battery replacement. We plan to apply to CMS and Medicare for insurance coverage of the device implantation and battery replacement costs, and to apply to Medtronic for device donation (Medtronic has already reviewed this proposal in their scientific grants committee and approved donation of the devices and replacement devices).

6) Protocol: Methodology to be used - The study will be a prospective blinded design. Subjects will include ten individuals with medication refractory and severely disabling TS. We expect to consent and screen 50 individuals in order to enroll ten. A total of 6/10 subjects (60%) will need to be “responders” as a result of the intervention (YGTSS motor tic subscale reduction of $\geq 40\%$) for this study to reach effectiveness criteria.

Inclusion Criteria

- The diagnosis of TS must be made by both a fellowship-trained movement disorders neurologist and a psychiatrist and must meet Diagnostic and Statistical Manual of Mental Disorders (DSM-V) criteria for a diagnosis of TS.
- Yale Global Tic Severity Scale (YGTSS; 100) must be $\geq 35/50$ for at least 12 months and the motor tic subscore ≥ 15 . The TS must be causing incapacitation with severe distress, self-injurious behavior, and/or quality of life disruption.

OCD, Depression, and ADHD are not exclusionary[63-65] provided tics are the major difficulty requiring surgical intervention.

- There are no gender criteria for this study.

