The combination of these analysis techniques in multiple brain regions (cortical and thalamic) allows for detection of thalamocortical interaction. Endogenous modulation of thalamocortical rhythmicity occurs during specific cognitive processes, several of which (e.g. sensorimotor gating, and focused motor action) have been implicated in the pathophysiology of TS[57]. This analysis will be performed for two reasons. First, these analyses may yield triggers detectable by the device by utilizing detection and signal analysis tools (i.e. spectral power estimation). This analysis will be performed for two reasons. First, these analyses may yield predictors detectable by the device by utilizing detection and signal analysis tools: line length trending, area-under-the-curve trending, and half-wave detection, applied in various logical combinations on single or multiple channels. Second, using an *a priori* limit on the multiple analysis methods will aid in assigning significance to any changes observed. This analysis will also allow us to conclude the total number of subjects in our cohort with gamma or other band oscillations. The analysis will allow us to examine whether there is an ECOG motor or pre-motor signal that can be used for responsive stimulation (detect in the ECOG and respond with DBS from the CM).

Specific Approaches for Aim 3: If an electrophysiological change or set of changes from baseline can be observed to preferentially accompany motor tics, across a given subject's data, with significance $p < 0.1$, it will be defined as a *predictor* for that

subject. Note that we do not require a high level of significance here; nor do we require the predictor to be entirely absent from baseline data. We assume that the consequences of a false positive (i.e., detection of the predictor without accompanying tics) are negligible. This is justified since the amount of stimulation that will be delivered responsively will in any case be less than that which would be delivered by their regular continuous stimulation. We will utilize available analysis tools to examine outcomes, but we will also report to the FDA on any new responsive stimulation detection and programming tools that may become available during the course of this protocol, and request permission to use them if appropriate.

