Subjects for whom predictors can be identified during acute physiological data collections in Months 1-5, as described above, will have a responsive DBS setting programmed for their six-month outcome testing. In responsive mode, the device may titrate the amplitude of stimulation within previously set comfort and safety levels, if tic signatures are not suppressed (i.e., until non-symptomatic brain signals are attained). If patients respond favorably during acute responsive testing, we will test chronic responsive stimulation for one month at a time (+/- 14 days), at some time point approved by the Principal Investigator between Month 6 and Month 36 (see visits 6.1-6.4 in schedule of events). The stimulation amplitude will be set to its optimal setting for chronic stimulation. The new patient programmer will allow patients to turn off responsive stimulation and switch back to standard continuous therapy. Subjects without a predictor will not have a chronic responsive setting.

Options for the Subject Once Specific Aims are Complete: Subjects may at any time during the study opt to terminate their participation and may also opt for

hardware removal. The investigator may continue to empirically adjust stimulation settings based on patient tolerance, and both short-term and long-term response. As long as the RC+S batteries are implanted, all subjects implanted will have the option for chronic or responsive stimulation depending on their individual preference and effectiveness of each technique. For subjects not under optimal control following 6 months of DBS therapy, we will offer open-label programming to search for the best parameters. Subjects who continue to receive active stimulation, will be followed by the PI and seen at yearly intervals. Patients will be able to be implanted with the standard Medtronic device after the study period once the RC+S is depleted. However, only the RC+S allow closed loop stimulation. As long as the subject is implanted with the RC+S device, the Principal Investigator will continue to follow and provide standard of care visits to subject throughout the duration of its battery life (labeled to last 9 years). These annual visits will be treated and billed as routine DBS checks. We will discuss with the subject the option of explanting their devices and pursuing insurance authorization to implant a standard Medtronic DBS device in CM for control of tic as needed.

13) Description of Power Analysis and Statistical Methods:

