Power Analysis: We will determine the effectiveness of DBS by comparing total tic score (YGTSS) at the six month time point to the pre-operative value for each subject. A 40% or greater reduction will be considered a successful response. The power to detect a statistical significance between a null proportion of 0.10 (this assumes that the true proportion of successful responders is 10%). The power analysis revealed that for an alternative proportion of .60 (i.e., 6 of 10 patients will show a

40% or greater reduction in motor tics at six months) there is a statistical power of 0.80 at an alpha level of .05. Therefore, we anticipate ten participants will be required for this study. The *power* procedure in Statistical Analysis Software (SAS), version 9.1 was used to conduct the power analysis. Data collected from this study will provide additional and currently unavailable data to inform power analysis of subsequent studies in Table 2 below.

Table 2. Power Analysis for Sample Size Effects

Table Power Analysis		Sample Size					
		8 patients		9 patients		10 patients	
Alternative proportion	Number of responders	Power	Number of responders	Power	Number of responders	Power	
.30	2	0.25	3	0.27	3	0.29	
.40	3	0.39	4	0.43	4	0.46	
.50	4	0.54	5	0.59	5	0.63	
.60	5	0.70	5	0.75	6	0.80	

General Analysis Approaches: The Wilcoxon signed rank test will be used to test for significant pre-post changes in numerical measures (e.g., YGTSS). Spearman correlations will be used to test relationships among numerical measures (e.g., neurocognitive measures, severity of tics and quality of life measures). Both the Wilcoxon signed rank and Spearman correlation tests are nonparametric procedures that are robust from data departures from normality and appropriate in the case of small sample sizes. All statistical tests will be two-sided and will be considered significant if p-values are less than 0.05. SAS software will be used to conduct all data analysis.

Specific Analysis Approach for Aim 1: We will determine the effectiveness of the “on condition” of DBS by comparing motor tic score (YGTSS) at the six month evaluation to the pre-operative value for each subject. A 40% or greater reduction will be considered a successful response. We will then test the hypothesis that the proportion of successful responders is greater or equal to (6/10) using the exact

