binomial test. We will compare the baseline motor YGTSS to the on DBS condition at six months (primary outcome). We will also perform comparisons of baseline to on/off/responsive conditions, and also comparisons of on/off conditions at six months as secondary analyses. To compare on versus off condition, we will form paired difference scores of YGTSS (YGTSS on minus YGTSS off) at six months and test for significance using the Wilcoxon signed rank test.

Specific Analysis Approach for Aim 2: We will first investigate rate and pattern changes in physiology and the possible correlation with clinical manifestation of motor tics by using exploratory data analysis techniques that will be graphical in nature. These exploratory techniques will include spectrograms and event related potentials. We will then conduct a preliminary time series analysis estimating fractal dimension, line length, and area-under-the-curve of the raw signal. The data obtained from these analyses will inform subsequent analysis and guide the development of statistical methods to analyze these types of data streams. Subsequent analysis will be more comprehensive, and will include time-frequency analysis of specific frequency bands, measures of coherence between channels containing movement related activity, and quantification of phase-amplitude coupling between frequency bands of interest. Any of these techniques has the potential to identify candidate predictors of tic onset.

Specific Analysis Approach for Aim 3: This protocol calls for testing an acute responsive DBS condition in subjects who reveal physiological predictors that can be set to sense tic by ECOG, and to respond to tic on the CM implanted device. It may also be possible to both sense and deliver stimulation from the CM DBS lead. Data will be analyzed using the Wilcoxon signed rank test. **We will collect physiology**

data and analyze the data, and test chronic responsive stimulation settings one month at a time for those subjects that respond well to the acute testion after Month 3.

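### Aim 3 asks whether responsive stimulation is an alternative to continuous DBS, but the plan offers only a signed-rank p-value in a subset of unstated size, with no margin, no interval and no settled comparator

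*Combined protocol and SAP*

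**What the plan says.** Section 5 (Purpose), item 3, sets the hypothesis that responsive stimulation is an alternative to chronic continuous stimulation. It says that both acute and chronic responsive outcomes will be judged against continuous stimulation. It also sets a gate for each patient: "If acute responsive stimulation leads to low side effects and comparable clinical outcomes for a patient, we will test chronic responsive stimulation".

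Section 12 (Study Summary, Details of the Protocol) instead attaches specific aim 3 to a comparison of the responsive response with pre-operative baseline.

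The analysis is in section 13:

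- Under Aim 3: "This protocol calls for testing an acute responsive DBS condition in subjects who reveal physiological predictors". Then: "Data will be analyzed using the Wilcoxon signed rank test". The sentence names no endpoint, comparator or p-value method.
- Under General Analysis Approaches: "All statistical tests will be two-sided and will be considered significant if p-values are less than 0.05".
- Under Aim 1, the secondary comparisons listed are baseline against each of the three modes, and on against off. Responsive against on is not listed.

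On numbers, section 6 gives the ceiling: "Subjects will include ten individuals with medication refractory and severely disabling TS". Section 12 (Specific Approaches for Aim 3) defines a predictor at p < 0.1 within a subject and adds: "Subjects without a predictor will not have a chronic responsive setting". How many subjects are expected at either stage is not stated.

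**The concern.** An aim framed as showing an alternative is, on efficacy, a question of whether responsive mode is not materially worse than continuous mode. A test of difference does not answer that. Without a margin or an interval, a non-significant result leaves open everything from no loss to a large one.

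The subset makes this sharper. If few subjects have a usable predictor, the named test may be unable to reach 0.05 whatever the differences are. The readout then says nothing in either direction.

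There is also a denominator question. The plan does not commit to reporting responsive-mode success out of all implanted subjects. A summary restricted to those who passed the selection steps would overstate how often responsive stimulation is an option.

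**Working it through.** **Plan's own figure.** There is none to reproduce for Aim 3. The only stated power (0.80 with ten subjects, section 13) belongs to the Aim 1 responder proportion.

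**Inputs from the document.** Two-sided alpha 0.05; Wilcoxon signed-rank test; at most 10 subjects; predictor required for acute testing; favourable acute response also required for chronic testing.

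**Inputs assumed.** The probability q that a subject has a predictor, the probability f of then entering the chronic stage, independence between subjects, and normally distributed paired differences for power.

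**1. Smallest attainable p-value.** With n non-zero, untied pairs, the most extreme result is all differences in one direction, so the minimum two-sided exact p is 2/2^n.

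| n | minimum p |
|---|---|
| 4 | 2/16 = 0.125 |
| 5 | 2/32 = 0.0625 |
| 6 | 2/64 = 0.031 |
| 8 | 2/256 = 0.0078 |
| 10 | 2/1024 = 0.0020 |

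For n of 5 or fewer, rejection at 0.05 is impossible. At n = 6 all six differences must have the same sign.

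**2. Dependence on the p-value method.** At n = 5 the statistic has mean 5×6/4 = 7.5 and variance 5×6×11/24 = 13.75 (SD 3.708). The uncorrected normal approximation gives z = 7.5/3.708 = 2.02, p = 0.043. With continuity correction, z = 7/3.708 = 1.89, p = 0.059. The method, which the plan does not name, can therefore decide significance at n = 5. At n = 4 even the uncorrected value is 0.068.

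**3. Chance of five or fewer pairs.** P(X ≤ 5) for X ~ Binomial(10, q) at the acute stage, or Binomial(10, q×f) at the chronic stage.

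| Stage | Assumption | P(≤ 5 pairs) |
|---|---|---|
| Acute | q = 0.5 | 0.62 |
| Acute | q = 0.6 | 0.37 |
| Acute | q = 0.7 | 0.15 |
| Acute | q = 0.8 | 0.03 |
| Acute | q = 0.9 | 0.002 |
| Chronic | 0.6 × 0.5 = 0.30 | 0.95 |
| Chronic | 0.8 × 0.6 = 0.48 | 0.67 |
| Chronic | 0.8 × 0.8 = 0.64 | 0.27 |

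**4. Power with six or more pairs.** At n = 6 power is Φ(d)^6 + Φ(−d)^6, where d is the true mean difference in SD units. For d = 0.5: 0.6915^6 + 0.3085^6 = 0.109 + 0.001 = 0.11. For d = 1: 0.8413^6 = 0.35, the second term being negligible. Values for n = 8 and 10 are from simulation of the exact test.

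| n | 0.5 SD | 1 SD | 1.5 SD |
|---|---|---|---|
| 5 | 0 | 0 | 0 |
| 6 | 0.11 | 0.35 | 0.66 |
| 8 | 0.19 | 0.61 | 0.92 |
| 10 | 0.28 | 0.78 | 0.98 |

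**5. Intervals.** The widest exact signed-rank interval has confidence 1 − 2/2^n. At n = 5 this is 93.75% (smallest to largest difference), so an exact 95% interval does not exist. At n = 6 it is 96.9%.

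**6. Denominator, as illustration.** Four successes among four selected subjects is 100% (exact 95% CI 40% to 100%). The same four out of ten implanted is 40% (12% to 74%).

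**The case against.** A reader might infer that the plan would declare responsive stimulation comparable whatever the data show. The document does not support that. Nowhere is a non-significant test said to mean comparability; in section 5 that idea is a gate for the individual patient to enter chronic testing. Against the baseline comparator of section 12, non-significance would mean no demonstrated effect, which counts against responsive mode. With six or more pairs, a consistent difference can reach significance.

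A reader might also take the tested set to be selected twice. That fits the chronic stage only. The signed-rank sentence follows directly on the acute condition, which has one selection step.

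Five or fewer pairs is an assumption, and several passages point to a larger acute set. The predictor rule is deliberately loose: "Note that we do not require a high level of significance here". If k independent features were screened with no true signal, a chance predictor would appear with probability 1 − 0.9^k: 0.34 at k = 4, 0.65 at k = 10, 0.88 at k = 20. The abstract reports that CM signals separate tic from voluntary movement, and section 12 counterbalances the three Month 6 conditions over all ten patients. None of this fixes the number, but an acute set near ten is possible.

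Section 12 (Specific Aim 2) also plans to count subjects in the cohort with gamma or other band oscillations. That is partial prevalence reporting, though not a count of responsive-mode success.

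Finally, section 7 presents responsive stimulation as something to explore, and section 12 puts the non-primary conditions under secondary analyses. No power is claimed for Aim 3, and the primary outcome is untouched. This stands, and it limits the severity.

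**Conclusion.** The point holds in limited form. The only inferential tool named for Aim 3 does not match its question, the comparator is unreconciled between sections 5 and 12, and neither the number of pairs nor a margin is stated. If five or fewer subjects qualify, the exact test is uninformative in both directions. That is likely at a 50% predictor rate and unlikely at 80%, and these rates are assumptions because the document gives none. The impossibility at exactly five pairs also assumes an exact p-value. With six to ten pairs, the test is weak for a half-SD difference, moderate for one SD at eight to ten pairs, and adequate only for larger ones at those sizes. No bias towards a favourable conclusion is written into the plan; what is missing is any stated way to reach a conclusion about comparability. Severity is below must-fix, because Aim 3 is exploratory or secondary and Aim 1 is unaffected.

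**What to change.** In section 13, Specific Analysis Approach for Aim 3:

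1. Reconcile sections 5 and 12. Make responsive minus continuous the Aim 3 contrast and responsive against baseline supportive. Name the tic scale, which must be one collected in each mode, and state the expected number of pairs.
2. Report each subject's paired difference and the Hodges-Lehmann estimate with an exact interval at its attained confidence level. Specify exact p-values. Treat the test as descriptive below six non-zero pairs. State that a non-significant result is not evidence of comparability.
3. Report counts out of all ten implanted subjects with exact 95% CIs, separately by stage: had a predictor; met the 40% criterion in acute responsive mode; entered the chronic stage; met the criterion in chronic responsive mode. Give reasons for non-entry. Show continuous-mode response alongside, so that subjects who did not respond to continuous stimulation are not counted as failures of responsive mode.

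The cost is SAP wording and a small extra analysis of data the plan already collects. The Aim 3 result will probably look less favourable, with wide intervals and smaller proportions.

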- The primary safety outcome will be defined as the serious adverse event (SAE) rate in patients compared to the SAE rate in patients implanted with the Medtronic DBS device for treatment of Parkinson's disease as drawn from published randomized studies[13, 67-71]. The intent is to show that the serious adverse event rate will not exceed the 95th percent confidence interval for the historical experience with the Medtronic DBS for Parkinson's disease. A 95% confidence interval for the SAE rate will be utilized for an analysis of data for 10 subjects at their three month visits due to the small sample size.
- The secondary outcome measure will consist of a review of the types, duration and frequency of non-serious adverse events. Therefore, all adverse events will be used as an additional measure in determining safety outcomes.
- The safety experience will be reviewed approximately every 6 months by the Data Safety Monitoring Board (DSMB). The DSMB will be informed of all serious adverse events and all mild adverse events which are potentially device related. The DSMB will designate each AE as mild or severe; as device related, uncertain to be device related or not device related; and as anticipated or unanticipated. The DSMB may employ a stopping rule for greater than 1 device related death or completed suicide.

Details of the Protocol:

- Following consent, subjects will be screened by the multidisciplinary team

and ethics panel to be certain all inclusion and exclusion criteria are met.

- Following approval by the multidisciplinary and ethics panel, subjects will undergo baseline studies and within four weeks will receive bilateral CM devices and bilateral ECOG devices.
- Stimulation will be turned on within one week (+/- 7 days) after the implant completion which will be approximately one month post lead implantation.
- All subjects will undergo once a month programming visits for months 1-6 (+/- 14 days, with the exception of Month 1, which has a +/- 7 day window). Additional visits may be needed to obtain optimization of settings.

Physiological data will be collected from both the CM thalamus and the ECOG strips during all protocol visits, and responsive parameters will also be tested. Subjects may also choose to come to the clinic for “unscheduled visits” as they deem necessary. The activities done at these visits will be at the discretion of the principal investigator.

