Data Safety Monitoring Board (DSMB): This study will have a designated DSMB composed of three members (A neurologist, a psychiatrist, and a non-neurological physician) without ties to the current study or any conflicts of interest. The DSMB will be charged with the duty of meeting every 6 months to discuss all of the AE's for the study.

The safety experience will be frequently reviewed by the Data Safety Monitoring Board (DSMB). The DSMB will be informed of all serious adverse events and all mild adverse events which are potentially device related in the opinion of the investigator. The DSMB will designate each AE as mild or severe; as device related, uncertain to be device related or not device related; and as anticipated or unanticipated.

Once the first subject is enrolled, the DSMB will meet approximately every 6 months in person, via teleconference, or electronically until all subjects have completed the 6

month primary outcome. The DSMB has the authority to suspend further enrollment pending investigation of safety concerns raised by SAEs occurring in the trial. The DSMB has a stopping rule for more than one death or more than 1 suicide deemed to be device related. The DSMB stopping rule for an individual subject would be a suicide attempt deemed potentially device related.

Adverse Event Reporting: Once a subject is enrolled into the study, continuous close monitoring will be conducted by the Principal Investigator (PI) in conjunction with the neurosurgeon and other investigators as well as the University of Florida's Institutional Review Board (IRB), through annual reports of progress and by immediate notification of serious and unanticipated adverse events by the PI to the IRB.

Stopping rules for the study have been established: This study will be suspended by the DSMB only if an unexpected and severe psychiatric or neurological complication occurs and they deem suspending or stopping the study appropriate. Specific examples that would warrant suspending the study include the following, only in the event that they do not reverse with adjustment or discontinuation of the DBS device:

- Severe worsening of symptoms
- Induction of severe difficult to treat depression

Additionally, the DSMB has a firm stopping rule for more than a single death or suicide attempt in the cohort during the 6 month post-operative period.

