therefore we will very likely need to switch to Summit RC+S eventually; this second-generation bidirectional (sense and stimulate) interface has a rechargeable battery, and an improved signal to noise ratio allowing detection of high frequency brain signals. It also has a greater flexibility in the implementation of adaptive algorithms. The RC+S can be considered an “upgrade” to the PC+S, as it still provides closed loop stimulation, but also is rechargeable, providing a much longer battery life (labeled as 9 years vs. approx. 2-3 years).

Adaptive stimulation with RC+S can occur in one of two modes: Distributed, in which the control algorithm resides on the researcher host computer (RHC), or embedded, in which control is accomplished within RC+S according to a preprogrammed algorithm. For in-clinic testing we will primarily use the distributed mode. During in clinic testing, ECoG and Cm-Pf LFP data will be streamed to the RHC to verify that neural correlates of tics can be detected. These detected events will then be used to responsively deliver DBS. We will also study markers of clinically optimized settings, by comparing signals to charge balanced stimulation settings that we know will not provide clinical benefit.

An adaptive control algorithm is embedded in RC+S. Prior to home use of adaptive stimulation, patients will be given and instructed on how to use the Clinician Therapy Module (CTM) and a tablet computer provided by the lab to interface with the CTM device which in turn communicates with the Summit RC+S. These devices allow switching off adaptive DBS and returning to open loop DBS.

Adaptive control algorithms: We will develop adaptive control algorithms using the Medtronic Research Development Kit. Since control algorithms will be based on each subjects’ personalized neural signatures of tic symptomology, we cannot specify exact

algorithms prior to obtaining recordings from RC+S. In general, we expect the controller to utilize spectral power from one or more frequency bands extracted from cortical and/or thalamic recordings. Our initial data points to significant deviations from baseline data during tics in the Cm-Pf that is not present during voluntary movements (see Figure 4). These features can be captured using power bands of low frequencies up to 8Hz.

[figure not shown]

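### Scheduled DSMB meetings end at the last subject's 6-month outcome, so that subject's chronic responsive stimulation, and possibly part of some earlier subjects', has no scheduled periodic review

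*Combined protocol and SAP*

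**What the plan says.** **DSMB meetings.** Section 17 (Monitoring Procedures, DSMB) starts the meetings at first enrolment and holds them about every six months, "in person, via teleconference, or electronically until all subjects have completed the 6" month primary outcome. No other text gives the meetings an end point. The opening paragraph of the same DSMB text sets the duty without an end: "The DSMB will be charged with the duty of meeting every 6 months to discuss all of the AE's for the study". So does section 12 (Study Summary): "The safety experience will be reviewed approximately every 6 months by the Data Safety Monitoring Board (DSMB").

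**Chronic responsive stimulation.** Section 5 (Purpose, third aim) places it "after the 6 month primary endpoint is reached but prior to Month 36". Specific Approaches for Aim 3, within section 12, has it "at some time point approved by the Principal Investigator between Month 6 and Month 36". The footnotes to both schedules in section 8 give the same range. Details of the Protocol (section 12) allows visits 6.1-6.4 to be done at the participant's home, and section 19 plans for home use: "Prior to home use of adaptive stimulation, patients will be given and instructed on how to use the Clinician Therapy Module".

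**What continues.** Sections 12 and 17 both state: "The DSMB will be informed of all serious adverse events". They add mild events that may be device related, and they have the board classify each event. Neither section puts an end date on this. Section 17 also provides annual reports to the IRB and immediate notice to it of serious and unanticipated events.

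**The concern.** The meeting calendar is tied to the primary outcome, but the study does not end there. Responsive stimulation in daily life begins afterwards. Section 19 says the control algorithms are built for each subject and cannot be specified beforehand. Section 14 says that the device with cortical strips has not yet been implanted in anyone with Tourette syndrome.

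The DSMB grades events, judges whether they are device related and can suspend the study. Once meetings stop, no date is set on which it would look at the accumulated events from this phase. Single notifications do not fully replace that: for mild events, section 17 leaves it to the investigator to decide first whether an event may be device related. In addition, the firm cohort stopping rule in section 17 covers only the six months after surgery.

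**Working it through.** The plan gives no figure to reproduce. The check compares the end of meetings with the responsive window.

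**1. Order of events.** Meetings end when the last subject completes the 6-month outcome. Under section 5, that subject's chronic responsive phase starts after the same outcome. All of it therefore follows the last scheduled meeting. This needs no calendar assumption.

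**2. Window for the last subject.** Window after meetings end = 36 − month of the outcome.
- On time: 36 − 6 = 30 months.
- Postponed: Details of the Protocol allows up to 12 months past the Month 1 visit, so about Month 1 + 12 = 13. Then 36 − 13 = 23 months.

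**3. Against the stated duration.** Section 5 plans five years (60 months), with subjects 9 and 10 implanted in Year 4 (study months 36-48).
- Month 6 falls at study months 36 + 6 = 42 to 48 + 6 = 54.
- Month 36 falls at study months 36 + 36 = 72 to 48 + 36 = 84, past month 60.
- Within five years, with the outcome on time, the window is 60 − 54 = 6 to 60 − 42 = 18 months.

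**4. Earlier subjects.** Section 5 plans 2, 3, 3 and 2 implants in Years 1 to 4. The month within each year is not given. Assume even spacing, so the last implant is at study month 45. Meetings then end at 45 + 6 = 51, or at 45 + 13 = 58 if the last outcome is postponed. Window after meetings = (implant month + 36) − end of meetings, floored at 0.

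| Subject | Implant (study month) | Months after meetings, last outcome on time | Months after meetings, last outcome postponed |
|---|---|---|---|
| 1-3 | 3, 9, 14 | 0, 0, 0 | 0, 0, 0 |
| 4 | 18 | 3 | 0 |
| 5 | 22 | 7 | 0 |
| 6 | 26 | 11 | 4 |
| 7 | 30 | 15 | 8 |
| 8 | 34 | 19 | 12 |
| 9 | 39 | 24 | 17 |
| 10 | 45 | 30 | 23 |

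With all implants at the start or all at the end of each year, the on-time case gives 0, 6, 18 and 30 months for subjects implanted in Years 1, 2, 3 and 4. Across these three timings, 7 to 8 of 10 subjects have some window after meetings end if the last outcome is on time, and 5 of 10 if it is postponed. Subjects 9 and 10 are affected in every case, by 17 to 30 months. These counts use the full window to Month 36, not the five-year limit.

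**5. Window against exposure.** The window is the time in which testing may be scheduled. Testing itself lasts up to four weeks (section 5) or up to four months (section 8 footnotes). Specific Approaches for Aim 3 limits it to subjects with an identified predictor and a favourable acute response.

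**6. Meetings in the gap.** At one per six months: 30/6 = 5; 23/6 = 3.8; 18/6 = 3; 6/6 = 1.

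**The case against.** A reader might infer that the novel mode runs with no independent oversight. The documents do not support that. The duty to inform the DSMB of serious and potentially device-related mild events has no end date. Neither does its power to suspend the study for an unexpected severe psychiatric or neurological complication, nor its individual-subject rule. The IRB is also independent of the investigators.

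A reader might also infer 30 months of unreviewed exposure. That figure is the longest eligibility window, and it runs past the five-year plan.

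The two open-ended sentences suggest that the end point may be loose wording and not a decision to stop review. That is fair, but neither sentence says that meetings continue past the 6-month outcome, and the one sentence with an end point does end them. The text needs reconciling either way.

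The risk can also be argued down:
- The plan expects responsive mode to deliver less stimulation than continuous mode, within preset limits.
- Subjects can switch back to continuous stimulation.
- Responsive settings are tried at the monthly visits and at Month 6, while meetings still run.
- Some early subjects may have their whole window covered.

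All of this stands and lowers the stakes. It does not put the last subject's chronic phase in front of a scheduled meeting.

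**Conclusion.** The point holds as a gap in scheduled periodic DSMB review, not in all independent oversight. It is certain for the last subject to reach the 6-month outcome, if that subject receives chronic responsive stimulation. For earlier subjects it depends on when the principal investigator schedules visits 6.1-6.4.

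The last subject's window after meetings end is up to 30 months, or about 23 with a postponed outcome. It is 6 to 18 months within five years, assuming Year 4 implantation and an on-time outcome. Exposure inside that window is much shorter. Whether testing is done at home does not change the gap.

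Two limits apply. The documents disagree on the length of chronic testing (four weeks or four months), and the Aim 3 analysis text in section 13 mentions Month 3 where other sections give Month 6. These passages must be reconciled; the conclusion rests on the Month 6 start. Part of section 19, just before the home-testing instructions, was not available, so any safeguard stated there could not be checked.

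This is an inexpensive improvement to safety oversight. It does not affect the primary analysis.

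**What to change.** In section 17, replace the end point of the meetings. Six-monthly DSMB reviews, electronic if preferred, should continue until the last subject eligible for chronic responsive stimulation has completed visits 6.1-6.4, and no later than Month 36 of the last subject. This lets the meetings stop early if no remaining subject is eligible. Align the opening DSMB paragraph of section 17 and the DSMB item in section 12, so that all three statements give the same end.

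The cost is up to about five further reviews by the existing three members, and fewer if the last outcome is postponed or responsive testing finishes early. Electronic meetings are already permitted, so no new staff or procedures are needed.
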